The primary study objective of this project is to investigate the effectiveness of a support group intervention using a solution-focused approach in reducing bullying, enhancing mental health, improving quality of life, and increasing general self-efficacy among school children in 5th-7th grade.

We hypothesize that the awareness of bullying created by the intervention, and the empowerment of children as contributors to the solution, will generate positive ripple effects benefiting all children in intervention schools. Furthermore, we hypothesize that children with a peer support group will exhibit lower levels of bullying, improved mental health, better quality of life, and increased general self-efficacy after the intervention compared to their baseline levels. We expect these effects to persist even after 6 and 9 months.

Aligned with the cluster RCT we will undertake a parallel process evaluation to assess the extent of the intervention coverage, whether the intervention was implemented according to the protocol and identify factors that hinder or aid the implementation of a support group intervention. For the process evaluation we will use the framework presented by the Medical Research Council guidelines focusing on the implementation (what is implemented and how), the mechanisms of impact (how does the delivered intervention produce change), and the context (how does the context affect implementation and outcomes)(Moore et al., 2015). The outline of the process evaluation is described later in the protocol.

Research questions: (prefix of p indicates primary research questions, prefix of s indicates secondary research questions)

pRQ1: To what extent do children in intervention schools report a reduction in **bullying** following a peer support group intervention compared to children in control schools receiving usual care, at intervention end and after 6- and 9 months?

pRQ2: To what extent do children in intervention schools report higher **quality of life** following a peer support group intervention compared to children in control schools receiving usual care, at intervention end and after 6- and 9 months?

pRQ3: To what extent do children in intervention schools report improved **classroom environment** following a peer support group intervention compared to children in control schools receiving usual care, at intervention end and after 6- and 9 months?

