pRQ4: To what extent do children with a peer support group report a reduction in **bullying** at the end of the intervention compared to their pre-intervention baseline level?

sRQ5: To what extent do children with a peer support group report improved **mental health** at intervention end compared to their pre-intervention baseline level?

sRQ6: To what extent do children with a peer support group report better **quality of life** at intervention end compared to their pre-intervention baseline level?

sRQ7: To what extent do children with a peer support group report increased **general self-efficacy** at intervention end compared to their pre-intervention baseline-level?

sRQ8: To what extent does the effects as measured in R1-R7 persist 6- and 9 months after intervention end compared with pre-intervention baseline level?

sRQ9: To explore the recruitment rate and factors associated with non-participation, on school, provider, and child level.

sRQ10: To describe whether the intervention was delivered according to protocol in terms of quality, quantity, adaptions and variations across schools and time.

[figure not shown]
sRQ11: To describe the intervention acceptability from children's, teachers, school nurses and residents' perspectives.

sRQ12: To investigate barriers and facilitators to intervention delivery and the mechanisms of impact.

Study design

This is a cluster randomized trial of children in 5th to 7th grade in Norwegian primary schools with randomization at school level. The cluster design is well-suited due to the significant risk of contamination between the groups with a regular RCT design. The study flow is presented in figure 1. Intervention schools will implement the SFA-model for reducing bullying, whereas the control schools will offer usual care according to national guidelines. The intervention is at two levels; (i) training of school nurses and school staff and raising awareness about the SFA-model among parents and students; for this part the outcomes will be measured at cluster-level, and (ii) implementing the SFA-model on individual participant level; for this part the outcomes will be measured on individual level in the intervention cluster only. The recruitment process, the intervention and the outcomes measured are described below.

Figure 1 Study flow for the Cluster randomized controlled trial

Methods

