The target population for the study are all school children in 5th-7th grade in primary schools in Asker, Moss and Lillestrøm municipalities in the central-eastern part of Norway. Primary schools with more than 200 students and with a school nurse appointed in at least 50% position are eligible for the study. Eligibility for having a support group established is based on the subjective experience of loneliness by the individual child and is defined as a negative emotional state caused by the discrepancy between the desired and actual social relationships, in line with Peplau et al (1).

Clusters and randomization procedure Since decisions about bullying interventions are typically made at the municipal level, we will begin the recruitment process of schools through enrolment of selected municipalities, as illustrated in figure 2. In selected municipalities consenting to participate, we will randomly invite 26 primary schools from the pool of eligible primary schools in these municipalities.

Figure 2. Illustration of the recruitment process of primary schools in xx, xxx and xxx municipalities in Norway

We will continue enrollment until the pre-identified number of schools is reached. The enrolled schools will be sorted by size and then block-randomized in a 1:1 ratio to either the intervention arm (hereafter referred to as intervention schools) or the control arm (hereafter referred to as control schools). A statistician not involved in the study will carry out the randomization procedure. After randomization, the schools will be informed about their assigned cluster and will receive more detailed information accordingly.

Sample size calculation *School level*: Based on the available literature, we anticipate that 6-10% of children in 5th -7th grade will report bullying (Krusell et al., 2019; Wendelborg, 2021). This proportion is expected to be reduced to at least 6 % in intervention schools' post-intervention. With a significance level at 5% and power at 80%, we will need 721 children in each arm. Accounting for additional variation, we would need 793 in each arm. We assume there will be three classes in each school with about 30 children in each class. Thus, we aim to include 26 schools (13 for each arm) to ensure that the study is sufficiently powered.

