Individual child level: The quality-of-life inventory KIDscreen-27 (28) has 5 domains and is scored from 0-100. For the domain "social support and peers", we anticipate a change of at least 3 points from baseline to 9 months (35). Further, when assuming a correlation of 0.7 to account for statistical dependencies (as the same child is assessed several times), and keeping significance level to 5%, we would need 55 children experiencing loneliness. To account for possible dropouts, we add additional 10% participants, i.e., 60 children.

Study procedure Essential information about the intervention, including the recruitment process and the continuation and follow-up phases will be shared with the municipality, students, parents, teachers and school nurses involved in the project. Written information about the option for support groups for children encountering challenges related to bullying at school will also be provided to parents. **Training Intervention Schools**: A group of two to three teachers or school nurses will participate in a three-day training program centered around the solution-focused approach and the support group model. This training will be led by *Adults for Children*, an organization possessing extensive expertise in implementing interventions within school settings. Following the training, the peer support group intervention will be initiated as soon as possible. **Control Schools**: In the control schools, preventive and health promotion services will be provided as usual and according to the guidelines set forth by the Norwegian Directorate of Health (29).

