Recruitment and follow-up of children experiencing bullying: The first initiative for a support group may come from the child itself or other individuals concerned about the child's well-being. Initiating a dialogue is the first step in building trust and determining if a support group could help. The child, together with the school nurse or teacher, will assess whether the support group is suitable for them. The school nurse and teachers will evaluate the child's situation carefully before recommending a support group, and if necessary, they will explore alternative follow-up options, particularly for children with complex challenges. The child experiencing bullying will not be part of the support group but will be involved in the selection of peers and will agree on what can be shared about their story with the group. The school nurse or teacher will collaborate with the child to identify 5-7 peers who could be suitable to join the group. The child is individually followed with weekly consultations with the teacher or school nurse, using an SFA-counselling approach.

Recruitment and follow-up of peers in the support group: Once peers are chosen, they are invited to the group. In the support group children are asked if they are willing to help another child. Clear boundaries will be set for peer supporters, specifically on what they may and may not share with others. They brainstorm actions they can take in the upcoming week. This transforms the group into a catalyst for improving a child's situation through small initiatives, using fellow students as a resource for change (Heitmann et al., 2022). Weekly consultations with the child and the supporting group are set up to monitor progress and brainstorm further enhancements. Peers are encouraged to concentrate on improvements and will receive acknowledgement for their progress. Sessions usually last 15-30 minutes weekly until improvement is seen. Studies indicate that the situation often improves rapidly, and in many cases, 3-5 weeks is sufficient (Heitmann et al., 2022; Kvarme, Heitman, et al., 2022; Kvarme et al., 2016; Ma et al., 2021). A comprehensive implementation manual has been developed for this intervention, and key steps are presented in table 1.

Table 1 Overview of all steps in the intervention.

The solution-focused counseling approach (SFA) is used in each step

Step 1: Meeting with the child who needs help. Create hope and identify participants for the support group.

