^aCorresponding research questions, ¹ KIDSCREEN-27 (Haraldstad et al., 2011), ^{II} Olweus' questionnaire (Olweus., 2013), ^{III} Strength and Difficulties Questionnaires (Goodman, 1997). ^{IV}General self-efficacy scale (GSE) (Roysamb et al., 1998)

This instrument assesses various aspects of physical and psychological well-being, autonomy, parent relations, social support, peer support and the school environment in children and adolescents aged between 8 and 18 years. The questionnaire has been validated for use in Norwegian school children (Haraldstad et al., 2011). Additionally, the student survey (Elevundersøkelsen, UDIR) will be administered at class-level. This survey includes inquiries about inclusion and well-being within the school setting. Mental health will be evaluated using the Strength and Difficulties Questionnaires, a validated tool for children between aged 2-17 years (Goodman, 1999). To measure self-efficacy, the General Self-Efficacy scale (GSE) will be utilized. This scale captures one's confidence in dealing with various demanding situations. A validated 5-item version of the GSE is available for use with Norwegian schoolchildren (Roysamb et al., 1998).

Table 3 Process evaluation outline and outcomes.

Indicators	Data sources	Timing
Recruitment		
Number of eligible schools invited and numbers consenting to participation.	National data, project data, including socio-demographic information (e.g., school size, ethnicity, SES)	At study start
Number of possible participants at each school (school children), number of participants invited to attend activities, actual number who do attend each activity	Attendance records	Ongoing throughout the intervention period
Number who drop out (Bullied children and peers)	Attendance records and a survey to explore reasons	Ongoing throughout the project
What was delivered		
Number of activities delivered in terms of use of resources, training sessions, and resource use, training conducted and attendance at training	School action plan, school environment questionnaire, interviews with teachers and school nurses (intervention deliverers)	Monthly collection of logs/records, brief interviews at regular intervals throughout project and final exit interviews and school environment questionnaire (pre-, post-)
Description of unintended events		

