Since all children in the study are younger than 16 years of age, consent will be sought from both parents and children who participate in the support group, followed by informed assent by children in all 5ths–7th grade in intervention and control schools. Informed consent will also be sought from parents and children participating in peer support groups (intervention schools). For parents of children in 5-7 classes who do not participate directly in the support group, passive consent will be obtained. In this part of the research, no personally identifiable information will be collected. The questionnaire is anonymous and no name, personal number or other directly identifiable information is asked. No one in the municipality, neither teacher, school nurse, administration staff or others will have access to answers that can be used to identify what individuals have answered. The results will be published through statistics showing how children and young people responded, or how different groups responded (boys or girls). Obtaining consent from all parents for students in the 5th–7th grade is a demanding process that will represent an additional burden and work for the schools. However, every student in 5th–7th grade will be informed of their right to refuse participation or to only assent to certain areas of the survey. They will also be informed that they are free to withdraw from the study at any time. The questionnaire will be conducted in the classroom with a teacher or school nurse present, and there will be minimal risk of being exposed to discomfort, stress, and injury. There will be no direct intervention or interaction. The researchers will conduct thorough research on ethical assessments of risks and develop concrete measures in terms of emergency response.

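### The supervision rule for the all-pupil survey lets a trained deliverer be in the room in intervention schools only, so reporting of the primary outcome could differ by arm

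*Protocol*

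**What the plan says.** **Who is in the room.** Safety Considerations describes the survey of all pupils in 5th to 7th grade: "The questionnaire will be conducted in the classroom with a teacher or school nurse present". The same section makes the survey anonymous, bars staff from answers that could identify a pupil, lets pupils refuse all or part of it, and says there is no direct intervention or interaction.

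**Who delivers the programme.** Study procedure, on intervention schools: "A group of two to three teachers or school nurses will participate in a three-day training program". The section on recruiting and following up children experiencing bullying adds: "The child is individually followed with weekly consultations with the teacher or school nurse". Table 3 gives as a data source "interviews with teachers and school nurses (intervention deliverers").

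**What differs by arm.** Study design has intervention schools implement the model, "whereas the control schools will offer usual care according to national guidelines". The intervention also includes "raising awareness about the SFA-model among parents and students". Allocation is open: "After randomization, the schools will be informed about their assigned cluster".

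**What is measured.** pRQ1 asks "To what extent do children in intervention schools report a reduction in" bullying, compared with children in control schools. By Table 2, pRQ1 to pRQ3 all rest on the all-pupil survey.

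**What is not covered.** The Risks section lists contamination, response rate, delay and PhD time. It does not list reporting bias. No section keeps trained staff away from survey supervision or standardises supervision across arms.

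**The concern.** The randomised comparison depends on what children say about a sensitive matter, in class, in an unblinded trial. Under the rule as written, the adult present in an intervention school may be one of the people running the programme. In a control school that adult has no programme to deliver. If pupils answer differently because of who is there, the difference enters one arm only and is indistinguishable from a change in bullying.

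Under-reporting that is equal in both arms would mainly cost power. The part that differs by arm biases the estimate, and the planned mixed models cannot separate it from a real effect. The planned difference is only 4 percentage points on a base of 10%, so even a modest difference in reporting would be a sizeable share of it. Survey conduct is already fixed in the Protocol, and an analysis plan cannot repair it afterwards.

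**Working it through.** **1. Reproduce the Protocol's figure.** Inputs from Sample size calculation: 10% (top of the stated 6–10%) versus 6%, 5% significance, 80% power. Sidedness is not stated; two-sided reproduces the figure.

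n = [1.960·√(2·0.08·0.92) + 0.842·√(0.10·0.90 + 0.06·0.94)]² / 0.04² = 720.9, so 721 per arm, as stated. Also 721 × 1.10 = 793, the inflated figure.

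**2. Assumed mechanism.** True bullying is 10% in both arms. A fraction u of bullied pupils does not report when a deliverer is present, and deliverers supervise a fraction f of intervention classrooms. The observed intervention rate is p₂ = 10% × (1 − u·f). The Protocol gives neither u nor f; all values below are assumptions.

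**3. Chance of a significant result favouring the intervention.** Φ[(0.10 − p₂ − 1.960·SE₀)/SE₁], with SE₀ the pooled and SE₁ the unpooled standard error, n = 721 per arm.

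Worked case u = 20%, f = 1: p₂ = 8%; SE₀ = √(2·0.09·0.91/721) = 0.01507; SE₁ = √[(0.0900 + 0.0736)/721] = 0.01506; (0.02 − 0.02954)/0.01506 = −0.633; probability 26%.

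Worked case u = 20%, f = 1/3: p₂ = 10% × (1 − 0.0667) = 9.33%; SE₀ = SE₁ = 0.01556; (0.00667 − 0.03051)/0.01556 = −1.53; probability 6%.

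| u | Every classroom (f = 1) | One third of classrooms (f = 1/3) |
|---|---|---|
| 10% | 9.0% vs 10%; chance 9.5% | 9.67% vs 10%; chance 4.0% |
| 20% | 8.0% vs 10%; chance 26% | 9.33% vs 10%; chance 6% |
| 40% | 6.0% vs 10%; chance 80% | 8.67% vs 10%; chance 14% |

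The nominal chance in this direction is 2.5%.

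**4. Clustering.** These figures treat pupils as independent. If the Protocol's 10% inflation is read as a design effect and 793 per arm is used, the effective size is 793/1.10 = 721 and the figures do not change.

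**5. Equal under-reporting, for contrast.** With a true 10% versus 6% and 20% non-reporting in both arms, the observed rates are 8% versus 4.8%. Power falls from 80% to about 70%, and no false effect is created.

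**The case against.** Several points on the other side are sound.

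- **Safeguards.** The survey is anonymous, staff cannot see identifying answers, pupils may skip areas, and the adult's role appears passive. This lowers the risk. It does not change who is present while a child answers.
- **Permitted, not planned.** A reader might infer that deliverers will run the survey. The Protocol does not say so. Only two to three staff per school are trained, and an untrained class teacher already satisfies the rule. The share of classrooms affected is unknown, so the 26% cannot stand alone.
- **Contact with the programme is narrow.** Looking for progress and praising it happens with the supported child and the 5–7 chosen peers, not with the whole class that answers the survey.
- **Control staff are not disinterested.** The background and ethics text say school nurses and staff everywhere are obliged to act on bullying or exclusion. What remains different is the delivery role.
- **Direction.** A reader might infer that the bias must flatter the intervention. The Protocol also expects greater awareness of bullying, which could raise reporting in intervention schools and hide a benefit.
- **Support-group questionnaires.** A reader might extend the criticism to the Olweus questionnaire, KIDSCREEN-27, SDQ and GSE. The supervision sentence concerns the all-pupil survey, no section says who supervises the others, and they serve within-arm questions.

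These points limit the size and certainty of the concern. None of them closes the gap in the rule.

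**Conclusion.** The concern holds as a weakness in how the survey is run. It is not an error of fact or a contradiction. The rule allows a trained deliverer to supervise reporting of the primary outcome in intervention schools, with no counterpart in control schools.

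The size and direction of any bias cannot be determined from the Protocol. With no true effect and 20% non-reporting when a deliverer is present, the chance of a false significant benefit runs from about 6% (deliverers in one third of classrooms) to about 26% (deliverers in all). Both figures rest on assumed rates, a 10% true rate in both arms and 721 pupils per arm. They show how sensitive a 4-point target is and do not predict what will happen. The change is worth making because it costs little and no analysis can recover what it protects.

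**What to change.** In Safety Considerations, state that at every wave and in both arms the all-pupil survey is supervised by an existing staff member who has not taken the three-day training and does not run support groups. Use one common read-out instruction in all schools, and record who supervised each session.

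The cost is minor rostering work. Because only two to three staff per intervention school are trained, another teacher can normally be used. Sample size, instruments and schedule do not change.

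The change removes only the part tied to a deliverer's presence. Pupils' and schools' general awareness of the programme and of allocation will remain, and should be acknowledged when the results are interpreted.

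Applying the same rule to the support-group questionnaires is an optional precaution, not the correction of a stated error.

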
Follow-up of participants

All study support group participants will receive post-study follow-up consultations with the school nurse or social teacher after the intervention. *Adults for Children*'s experience with research involving children and will carefully address the ethical responsibilities, including how to inform children, in their 3-days training program. Participants from *Adults for Children* and the researchers are available for teachers, school nurses, children, and their parents throughout the study. A safety plan is also prepared for additional support should be necessary after the study concludes. If the intervention yields positive effects, all control schools will be invited to implement the intervention as per protocol soon after the conclusion of the study.

Data protection and statistical analysis

We will seek ethical approval for the study from the Regional Ethical Research Committee (REC) in South-East Norway and ensure compliance with data privacy regulations in line with NSD and EUs privacy regulation GDPR. Data will be collected through and stored in the secured server *Tjenester for Sensitive Data* (TSD), integrated solution for collecting and storing sensitive data, managed by the University of Oslo. This includes recording of interview-data through the use of Nettskjema-diktafon in TSD. This is in line with OsloMet's standards for confidentiality and data protection. A risk assessment with appropriate actions will be conducted prior to study implementation.

Baseline data will be presented descriptively. We will use 1600 children (9 schools in each arm) for comparison between intervention- and control schools on school-level. Generalized mixed models (GLM)

for repeated will be used to explore intervention outcomes on individual level for children who were targeted for support groups. GLM will also be used to analyse possible differences on school level. The results will be reported as the estimated between group changes with 95% confidence intervals.

For the process evaluation, descriptive statistical analysis of quantitative data and content analysis of qualitative data will be carried out.

Quality assurance

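### The sample size section plans 26 schools (13 per arm), but the analysis section compares 9 schools per arm (18), and nothing reconciles the two

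*Protocol*

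**What the plan says.** Under Methods, the paragraph on clusters and randomisation says that "we will randomly invite 26 primary schools from the pool of eligible primary schools in these municipalities" and adds: "We will continue enrollment until the pre-identified number of schools is reached". Enrolled schools are then randomised 1:1.

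The school-level sample size paragraph builds up in four steps. It starts from 721 children per arm, for 80% power at the 5% level. It then raises that number: "Accounting for additional variation, we would need 793 in each arm". Next it takes a school to have three classes of roughly 30, which makes about 90 children per school. From this it concludes: "Thus, we aim to include 26 schools (13 for each arm) to ensure that the study is sufficiently powered".

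The section Data protection and statistical analysis then gives a different size for the same comparison: "We will use 1600 children (9 schools in each arm) for comparison between intervention- and control schools on school-level".

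No part of the protocol says that 8 schools are a reserve, that they allow for withdrawal or non-response, or that the analysis uses a subset of the randomised schools.

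**The concern.** In a cluster randomised trial the number of clusters is a core design figure, and the protocol gives two values for it. One is tied to inclusion and to power. The other sits in the analysis text and describes which data will be used. The comparison concerned is the one between intervention and control schools on bullying, quality of life and classroom environment.

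Two things are at stake. First, if 26 schools are randomised, the analysis sentence taken at its word leaves up to 8 of them out and gives no rule for choosing them. Dropping randomised clusters would undermine the randomised comparison. The text does not say this is intended, but its wording leaves the reading open. Second, if 9 per arm is the intended size, the plan has almost no room for non-response at its own planning value of 90 children per school. Under Safety Considerations every child "will be informed of their right to refuse participation or to only assent to certain areas of the survey".

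**Working it through.** **Inputs from the protocol.** Bullying is anticipated at 6–10% and is to fall to 6% in intervention schools; significance level 5%, power 80%; 721 children per arm, then 793; three classes of about 30, so about 90 children per school; 26 schools in one section, 18 in the other. The protocol states neither the sidedness of the test nor an intracluster correlation (ICC).

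**Step 1: reproduce 721 and 793.** The pooled two-proportion formula with 10% vs 6% (mean 8%), two-sided 5%, 80% power, is

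n = [1.96 x sqrt(2 x 0.08 x 0.92) + 0.8416 x sqrt(0.10 x 0.90 + 0.06 x 0.94)]² / 0.04² = 720.9, so 721 per arm.

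793/721 = 1.10, so the allowance for additional variation is a 10% inflation. Both figures reproduce.

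**Step 2: from children to schools.**

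- 793/90 = 8.81, so 9 schools per arm.
- 2 x 793 = 1586, close to 1600; 1600/18 = 88.9 children per school.

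The analysis section therefore matches the sample size section's own inputs. The 13 does not follow from them: 13 x 90 = 1170 per arm, and 1170/793 = 1.48.

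**Step 3: what the 13 could stand for.** Any of these would fit, and none is stated:

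- non-response: 793/13 = 61 of 90 children per school, 68%;
- school withdrawal: 9 of 13 schools kept, 69%;
- a larger allowance for clustering: 1170/721 = 1.62 instead of 1.10.

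The figure of 1600 children alone would fit 26 schools (1600/26 = 61.5 per school, 68% of 90). The count of 9 schools per arm does not.

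**Step 4: what the difference does.** Power uses the same normal approximation as Step 1, with effective n = n/1.10 and full response. The ICC limit is the value at which n equals 721 x (1 + 89 x ICC).

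| | 13 schools per arm | 9 schools per arm |
|---|---|---|
| Children per arm at full response | 1170 | 810 |
| Response needed for 793 per arm | 793/1170 = 67.8% | 793/810 = 97.9% |
| Power, 10% vs 6% | 92.6% | 80.8% |
| Highest ICC that keeps 80% power | (1170/721 − 1)/89 = 0.0070 | (810/721 − 1)/89 = 0.0014 |

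**Step 5: total held at 1600 children (800 per arm).** If the 1.10 is read as a design effect, the implied ICC is (793/721 − 1)/89 = 0.0011.

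- 13 schools of 61.5: effective n = 800/(1 + 60.5 x 0.00112) = 749, power 81.5%.
- 9 schools of 88.9: effective n = 800/(1 + 87.9 x 0.00112) = 728, power 80.4%.

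With the number of children fixed, the number of schools hardly changes power at so small an ICC.

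**The case against.** The strongest reply is that the analysis sentence only restates the calculated minimum, or is left over from an earlier count, and was never a rule for dropping schools. Other text supports this. Table 2 gives the Study 1 population as all students, the research questions compare children in intervention and control schools without naming a subset, and the protocol commits to CONSORT for cluster trials. This reading is plausible and probably right. It explains how the conflict may have arisen but does not remove it, because the protocol never calls 9 or 1600 a minimum.

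A second reply is that 26 is the number invited and 9 per arm is what remains after losses. The sample size paragraph speaks of including 26 schools, and ties that number to power. The risk section meets low response with recruitment measures, not with reserve schools.

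The third reply concerns size. Both counts meet 80% power on the protocol's inputs, and with 1600 children fixed the gap is about one percentage point. That stands. The power figures also rest on inference: reading the 1.10 as a design effect is an assumption, and the normal approximation ignores the small number of clusters. With a t reference on 2 x 9 − 2 = 16 degrees of freedom and the same inflation, power is about 76% for 9 schools per arm; on 24 degrees of freedom it is about 90% for 13. That correction makes 9 schools look weaker.

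The 98% response figure depends on 90 children per school. At an assumed 100, 110 or 120, 9 schools per arm would need 88%, 80% or 73%.

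Finally, a statistical analysis plan may define the analysis population. It cannot agree with both school counts, so the conflict has to be settled in the protocol.

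**Conclusion.** The concern holds and should be fixed. The protocol gives 26 schools in one section and 18 in another for its primary school-level comparison, a difference of 8 in 26 (31%), without explanation. This needs no calculation. The arithmetic adds that 9 per arm and about 1600 children are what the stated inputs produce, and that 13 is the figure without a derivation.

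It is not shown that the trial is underpowered, or that any school will be excluded. What differs is the margin: 67.8% against 97.9% response needed at 90 children per school, and tolerance of an ICC up to about 0.007 against 0.0014. These are single-time-point figures for 10% vs 6%, two-sided 5%, and the power and ICC figures assume full response. They are only indicative for the planned mixed model.

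**What to change.** In the sample size section, state one number of schools per arm and show how it follows from 793 children per arm, naming any allowance for non-response, school withdrawal or clustering.

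In the statistical analysis section, replace the sentence on 1600 children with: *The school-level comparison will include all randomised schools and all responding children, analysed in the arm to which the school was allocated.* If 9 per arm or 1600 is a minimum after expected loss, say so in the sample size section and do not use it to define who is analysed.

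The cost is two sentences. If 26 schools are kept, no further schools or data are needed. If 18 is the intended number, the target in the sample size section changes and the small allowance for non-response must be justified.
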